Metformin (N,N-dimethylbiguanide) has been used widely for many decades and has a well-characterized side effect profile. Initially this drug was developed for type II diabetes and insulin resistance; however, there has been recent renewed interest in Metformin given its anti-oxidant effects and potential protective effects, as observational studies have demonstrated a decreased incidence of breast cancer, lung cancer, colorectal cancer, and hepatocellular carcinoma in patients treated with Metformin, possibly through AMP-kinase activation and mTOR inhibition (summarized in ¹⁰). Relevant to this study, Metformin has also demonstrated aldehyde scavenging capabilities. Recent preclinical models both in FA cell lines and in FA mice have demonstrated that Metformin improved the platelet count and ANC in FA mice and that this may be mediated by increasing the percentage of cells in quiescence and by improving DNA repair, as Metformin treated fibroblast cells had decreased numbers of spontaneous radials and breakage.¹¹

Based on these data, we propose a single institution, open-label, single arm pilot study of Metformin in patients with Fanconi Anemia and cytopenias with the primary endpoint of hematologic response. This study will also assess safety, tolerability, and the biologic effects of Metformin in patients with FA.

- ↑ Clinic visit, labs, and marrow evaluation
- ↑ Clinic visit, labs, and PK samples (when available); otherwise, phone call and local labs
- ↑ Local labs
- ↑ Phone call and drug diary review
- ★

TABLE OF CONTENTS

1. OBJECTIVES	5
1.1 Study Design	5
1.2 Primary Objective	5
1.3 Secondary Objectives	5
1.4 Exploratory Objectives	5
2. BACKGROUND	6
2.1 Fanconi Anemia	6
2.2 Metformin	6
2.3 Rationale for evaluation of Metformin in Fanconi Anemia	8
2.4 Rationale for planned correlative studies	9
3.5 Overall summary of rationale	10
3. PARTICIPANT SELECTION	11
3.1 Inclusion Criteria	11
3.2 Exclusion Criteria	12
4. ENROLLMENT PROCEDURES	13
4.1 General Guidelines	13
4.2 Evaluable Patients	13
5. TREATMENT PLAN	13
5.1 Treatment Regimen	13
5.2 Agent Administration	15
5.3 Study Visit Procedures	15
5.4 General Concomitant Medication and Support Care Guidelines	17
5.5 Criteria for Taking a Participant Off Protocol Therapy	18
5.6 Duration of Follow Up	19
5.7 Schedule of Assessments	19
6. HEMATOLOGIC RESPONSE CRITERIA	21
7. ADVERSE EVENTS: LIST AND REPORTING REQUIREMENTS	22
7.1 Adverse Event Management	23
7.2 Dose Modification	23

1. OBJECTIVES

1.1 Study Design

This is a pilot pediatric single center investigator-initiated clinical trial in Fanconi Anemia.

1.2 Primary Objective

- 1.2.1 To evaluate the hematologic response.

1.3 Secondary Objectives

- 1.3.1 To evaluate the hemoglobin, RBC transfusion requirements, platelet count, and absolute neutrophil count.
- 1.3.2 To evaluate the hematopoiesis through evaluation of marrow cellularity and hematopoietic progenitor colony assays.
- 1.3.3 To evaluate the safety in Fanconi Anemia patients.
- 1.3.4 To describe the pharmacokinetics in Fanconi Anemia patients.
- 1.3.5 To describe the tolerability in this population at the target dose for 6 months duration.

1.4 Exploratory Objectives

- 1.4.1 To describe the change in aldehyde-mediated toxicities in peripheral blood and bone marrow samples before and after Metformin treatment (in collaboration with [name], University of North Carolina).
- 1.4.2 To describe the changes in chromosomal breakage (in collaboration with [name], DFCI Fanconi Anemia Center).
- 1.4.3 To describe changes in micronuclei formation in a buccal swab assay.
- 1.4.4 To describe changes in CD34+ hematopoietic stem/progenitor cell cycling.
- 1.4.5 To describe fasting glucose and fasting insulin levels.
- 1.4.6 To describe genotype:phenotype associations using whole exome sequencing and targeted gene analyses.

2 BACKGROUND

2.1 Fanconi Anemia

Fanconi Anemia (FA) is an inherited bone marrow failure disorder characterized by a DNA repair defect. FA patients have a high risk of developing aplastic anemia and have a predisposition to develop malignancies including MDS, AML, and solid tumors, namely squamous cell carcinomas of the head, neck, GI tract, and vulva. Many patients have congenital anomalies including renal abnormalities, skeletal dysplasias, and skin abnormalities. Allogeneic hematopoietic stem cell transplantation can cure the hematologic complications of FA; however, patients who undergo stem cell transplantation may have an increased risk of developing solid tumors due to the effects of chemotherapy and radiation used in transplant conditioning regimens as well as the effects of inflammation from mucosal damage and from GVHD.¹ Donor availability also limits transplant options for a subset of patients.

For patients unable or unwilling to undergo a hematopoietic stem cell transplant, androgens such as oxymethalone or danazol can improve blood counts in many patients with FA, though a subset of patients fail to respond or relapse after an initial response. Patients on androgens remain at risk for leukemia. Androgens are associated with significant side effects including transaminitis, cholestasis, peliosis hepatitis, hepatic adenomas and carcinomas, and virilization. Hepatic complications of androgens may increase the risk of a subsequent hematopoietic stem cell transplant. Safe oral agents to treat bone marrow failure without increasing the risk of malignancy and to target the underlying DNA repair defect are urgently needed.

In recent years, intensive scientific laboratory research by a collaborative group of leading FA investigators has identified potential agents, including Metformin and TGF- β inhibitors, that improve hematopoiesis in vitro and in animal models while providing protection from DNA damage. These promising preclinical findings need to be studied in clinical trials to develop new treatments for FA patients.

2.2 Metformin

Metformin (N,N-dimethylbiguanide) is an FDA approved drug with a well-characterized side effect profile with low toxicity. Metformin was initially developed as a drug for type II diabetes and insulin resistance. There has been recent renewed interest in Metformin given its anti-oxidant effects, and Metformin has been demonstrated to decrease the incidence of certain types of solid tumors in patients taking this medication in observational studies. It has been hypothesized that these anti-cancer properties may be due to AMP-kinase activation and mTOR inhibition.^{6-9,10} In addition, 39% of patients with FA on screening had glucose and insulin handling abnormalities, making Metformin an attractive drug for this patient population as Metformin may improve both hematopoiesis and insulin resistance in this population.¹⁰ Although there have been rare instances of lactic acidosis with Metformin treatment, a Cochrane review from 2010 demonstrated that there were no cases of lactic acidosis from 347 comparative trials and cohort studies representing 70,490 patient-years of Metformin use.²⁵

2.2.1 Preclinical pharmacology and toxicity studies of Metformin

Carcinogenesis and Mutagenesis studies:

Long-term carcinogenicity studies have been performed in rats (dosing duration of 104 weeks) and mice (dosing duration of 91 weeks) at doses up to and including 900 mg/kg/day and 1500 mg/kg/day, respectively. These doses are both approximately four times the maximum recommended human daily dose of 2000 mg based on body surface area comparisons. No evidence of carcinogenicity with Metformin was found in either male or female mice. Similarly, there was no tumorigenic potential observed with Metformin in male rats. There was, however, an increased incidence of benign stromal uterine polyps in female rats treated with 900 mg/kg/day. There was no evidence of a mutagenic potential of Metformin in the following in vitro tests: Ames test (*S. typhimurium*), gene mutation test (mouse lymphoma cells), or chromosomal aberrations test (human lymphocytes). Results in the in vivo mouse micronucleus test were also negative. Fertility of male or female rats was unaffected by Metformin when administered at doses as high as 600 mg/kg/day, which is approximately three times the maximum recommended human daily dose based on body surface area comparisons (Metformin label).

Pregnancy: Pregnancy Category B.

Nursing mothers: Studies in lactating rats show that Metformin is excreted into milk and reaches levels comparable to those in plasma. Similar studies have not been conducted in nursing mothers (Metformin Label).

2.2.2 Prior clinical experience with Metformin

Pediatric studies for obesity are included in a meta-analysis of 5 studies which demonstrated that Metformin treatment led to a decrease in BMI by a mean of 1.42kg/m² over placebo treatment. This meta-analysis did not demonstrate strong evidence of a treatment effect on fasting glucose. The most common side effect was gastrointestinal (20-30%) and was more common in the treatment Metformin group as compared to the placebo groups (risk difference of 10-14%).¹²

Another systematic review and meta-analysis of 9 randomized controlled trials for obesity in adolescents aged 12 to 19 on Metformin doses of 1000mg to 2000mg daily did not demonstrate a statistically significant difference in frequency of gastrointestinal adverse events in the Metformin group as compared to the placebo group.¹³ This study also demonstrated a mean decrease in BMI by 1.42mg/m² in the treatment group as compared to the placebo control group, and demonstrated decrease in hyperinsulinemia (-9.9uU/mL) in the treatment group as compared to the control group.

A recent systematic review details the studies of Metformin in obese non-diabetic children and adolescents.¹⁴ A number of studies included in this review have documented the safety and tolerability of Metformin below 10 years of age.¹⁵⁻¹⁹ None of these studies demonstrated any change in the adverse effect profile when compared to patients older than the age of 10. The

most common side effects as in older patients were gastrointestinal side effects.

Metformin has also been studied in a population of patients aged 6 to 17 years with weight gain associated with atypical antipsychotic medications, with doses of 500mg BID for children up to age 10 and 850mg BID for patients 10 to 17 years of age. Metformin decreased BMI z scores by -0.1 in the treatment group as compared to the control group and overall was well tolerated with 5 patients (out of 61 randomized patients) who discontinued treatment, 4 due to agitation and 1 due to sedation. Patients who received Metformin treatment had a nonsignificant higher incidence of gastrointestinal side effects, though these were experienced for significantly higher duration of treatment (25.1% versus 6.8%).²⁰

Metformin has also been tested in patients down to the age of 4 in assessing changes in markers of insulin resistance and inflammation. It was well tolerated other than diarrhea in 35.7% of the patients during week 1, which disappeared in all cases but one, and no patients discontinued the drug due to side effects. No other serious adverse events were noted.²¹

Metformin has been tested in 10 non-diabetic pediatric patients with steatohepatitis with 500mg BID dosing for 24 weeks in a phase II clinical trial and demonstrated statistically significant improvement in AST and ALT, liver fat, and insulin sensitivity as well as quality of life. Although 3/10 patients developed gastrointestinal side effects, all subjects subsequently tolerated Metformin treatment without GI side effects by 4 weeks. There were no episodes of acidosis.²²

Metformin has been demonstrated to decrease cancer risk in adult patients with type II diabetes in a population-based cohort study. Patients who had received more than 360 daily doses of Metformin monotherapy had a decrease in cancer risk by a hazard ratio of 0.4 [0.22-0.66], and patients who received more than 1080 defined daily doses of Metformin had a hazard ratio of 0.27 [0.09-0.84].²³

2.3 Rationale for evaluation of Metformin in Fanconi Anemia

2.3.1 Preclinical activity of Metformin in Fanconi Anemia

Our collaborators at the Oregon Health Sciences University led by [name] extensively studied the effects of Metformin in an FA mouse model and in FA patient-derived cells and determined that Metformin administration both improves hematopoiesis and reduces DNA damage. Their data, which was recently published in Blood, is summarized below.¹¹

In this study, FANCD2^{-/-} mice were fed Metformin (roughly 65% of the maximum dose in humans, or 300mg/kg/day) for 6 months. Serial blood counts demonstrated improvement in platelet counts (p <0.05), hemoglobin (p <0.005), and WBC in the Metformin-treated mice.

Since marrow failure and cytopenias may be triggered or exacerbated by physiologic stress, the researchers tested whether Metformin could protect against hematologic abnormalities in mice treated with poly(I:C), which induces inflammation. Interestingly, Metformin provided some protection from the poly(I:C)-induced aplastic anemia when compared to treatment with placebo (p<0.01). Metformin-treated FANCD2^{-/-} mice treated with poly(I:C) demonstrated preservation

of spleen colony formation (CFU-S) following transfer of bone marrow from these mice into irradiated recipients. In contrast, the FA mice exposed to poly(I:C) without Metformin had dramatically reduced ability to form CFU-S. This experiment suggests that the hematopoietic stem/progenitor cells are relatively preserved with Metformin treatment.

Prior data suggest that Metformin may have tumor-protective effects. To assess potential effects of Metformin on tumorigenesis, the cancer-prone FANCD2-/- Tp53+/- mice were treated with Metformin or placebo, and followed for tumor development and for survival. The FANCD2-/- Tp53+/- mice had a longer latency period until tumor formation (first tumors were found at 142 days as compared to 244 days) and longer tumor-free survival time (405 days as compared to 368 days), suggesting that Metformin delays tumor formation in FANCD2-/- Tp53+/- mice. This effect was not observed in the FANCD2+/- Tp53+/- mice, suggesting that Metformin's effect on tumor formation in these mice might be specific to the FANCD2-/- mice.

The preclinical data generated by our colleagues at OHSU and described above suggest that Metformin treatment of FA cell lines *in vitro* and FA mice *in vivo* improves hematopoiesis both at baseline and when stressed with poly(I:C) administration and may do so through improvement in aldehyde handling, decreased chromosomal breakage and radial formation, and increased quiescence. FA mice have a modest improvement in tumor free survival with a Metformin diet as compared to a placebo diet.

2.4 Rationale for planned correlative studies

The mechanisms causing bone marrow failure in patients with Fanconi Anemia have largely been studied in murine models and patient-derived cells *in vitro*. Biomarkers of marrow failure in Fanconi Anemia have not been well studied, and a descriptive study of biomarkers associated with treatment response may advance our understanding of marrow failure in these patients. Although the basic science understanding of Fanconi Anemia has progressed rapidly over the past decade, the clinical treatment options have not progressed at the same rate.

The mechanisms promoting bone marrow failure in FA have been postulated to include aldehyde-mediated toxicity, stem cell exhaustion, and DNA damage. The preclinical data with Metformin suggests that Metformin may be improving hematopoiesis in FA mice and cell lines by protecting against aldehyde-mediated toxicity, promotion of stem cell quiescence, and reduction of DNA damage.¹¹

- 1) Both guanine derivatives of aminoguanidine and Metformin were able to protect FA-G patient derived lymphoblastoid cells from exogenous formaldehyde and MMC toxicity. A similar experiment in which endogenous formaldehyde levels were increased by administering a small molecule inhibitor of Adh5 also demonstrated similar results in which FA-A derived fibroblast cells were protected from chromosomal breaks and radial formation by administration of Metformin ($p<0.0001$ and $p<0.001$).
- 2) Metformin induced cell cycle quiescence of the HSC compartment in FANCD2-/- mice as compared to control mice. It is hypothesized that quiescence of stem cells may decrease the harmful effects of poly(I:C) induced cycling of HSCs.

- 3) FA patient cells demonstrate high rates of radial chromosome formation and chromosomal breaks, and treating FA-A patient derived fibroblast cells demonstrated decreased radial and chromosomal breakage formation when treated with Metformin as compared to placebo. Another guanidine derivative, aminoguanidine, was also tested and shown to have a similar effect.

Therefore, correlative studies will describe whether Metformin changes the quiescence of hematopoietic stem cells, leads to a change in the expression of genes in the DNA damage pathway, alters the chromosomal breakage test results after treatment with MMC or DEB, affects the formation of micronuclei in a buccal cell assay, and alters patients' aldehyde handling.

2.5 Overall summary of rationale

Since Fanconi Anemia is a rare disease, a small prospective pilot study was chosen as the study design. Although the small sample size and open-label single-treatment arm design of this study will not be able to definitively determine clinical benefit of Metformin treatment in this patient population, this study will provide additional information regarding safety, tolerability, and preliminary efficacy of Metformin in FA patients and may provide the basis for a larger controlled clinical trial.

As Metformin would be used as a chronic medicine if it improves hematopoiesis, it is necessary to assess safety and tolerability of this medicine over several months. As our goal is to improve the understanding of the mechanisms by which Metformin may improve hematopoiesis, biological correlative studies will be integrated into the clinical trial with blood and marrow collection and analysis and may lead to additional hypotheses, which can in turn become the bases for additional potential therapies in this patient population.

There is urgency to run this trial since Metformin is available for clinical use and could easily be given off-study, in which case safety and efficacy will remain unclear, and there is a high unmet medical need for safe and tolerable medical therapies for patients with FA and marrow failure as there are no established treatment options for marrow failure other than bone marrow transplantation, androgen therapy, or hematopoietic growth factor therapy. Metformin is anticipated to be safe and tolerable in this patient population given the prior published clinical experience using this medication in various patient population including pediatric patients with type I and II diabetes and obesity, and Metformin is currently being used in trials for advanced solid tumors. The doses tested in this trial are doses which have either been FDA approved (ages 10 years and older), or doses which have been previously tested and well tolerated (ages 6-10 years).

3 PARTICIPANT SELECTION

3.1 Inclusion Criteria

3.1.1 Age \geq 6 years and \leq 35 years

3.1.2 Lansky/Karnofsky performance status \geq 50% for patients \geq 16 years of age and Lansky \geq 50% for patients $<$ 16 years of age (see Appendix A)

3.1.3 Diagnosis requirement

3.1.3.1 Participants must have a clinical diagnosis of Fanconi Anemia.

3.1.3.2 Participants must have confirmed DEB/MMC testing to document diagnosis of Fanconi Anemia.

3.1.4 Patients must have at least one of the following cytopenias:

- Hemoglobin $<$ 10g/dL
- Platelets $<$ 100k/uL
- Absolute neutrophil count $<$ 1000/uL

3.1.5 Participants must have normal organ function as defined below:

3.1.5.1 Hepatic Function

- Total bilirubin \leq 1.5 x upper limit of normal for age
- ALT/AST \leq 135 U/L

3.1.5.2 Renal Function

- A serum creatinine based on age/gender as follows:

Age	Maximum Serum Creatinine (mg/dL)	
	Male	Female
1 to $<$ 2 years	0.6	0.6
2 to $<$ 6 years	0.8	0.8
6 to $<$ 10 years	1	1
10 to $<$ 13 years	1.2	1.2
13 to $<$ 16 years	1.5	1.4
\geq 16 years	1.7	1.4

AND

- Creatinine clearance \geq 60 mL/min/1.73 m² for participants with creatinine levels above institutional normal

3.1.5.3 Normal cardiac status as documented clinically, otherwise they will need an echocardiogram prior to enrollment

- 3.1.5.4 Serum bicarbonate must be >17.
- 3.1.5.5 Participants of child-bearing or child-fathering potential must agree to use adequate contraception (hormonal birth control; intrauterine device; double barrier method; or total abstinence) throughout their participation, including up until 30 days after last dose of Metformin.
- 3.1.6 Ability to understand and/or the willingness of the patient (or parent or legally authorized representative, if minor) to provide informed consent, documented using an institutionally approved informed consent procedure

3.2 Exclusion Criteria

- 3.2.1 Patients must not have undergone prior bone marrow transplantation.
- 3.2.2 Patients must not have very severe aplastic anemia at the time of enrollment which would require bone marrow transplantation (as defined by at least 2 out of the following 3: ANC <200/uL, platelets <20k/uL, absolute reticulocyte count <40k/uL). If patients are not eligible for a transplant and otherwise meet the inclusion/exclusion criteria, then they may enroll in this trial.
- 3.2.3 Patients must not be taking any other concurrent medications to improve their hematopoiesis such as androgens or growth factors such as G-CSF, EPO, or TPO mimetics. If any of these prior therapies, including androgens, have been taken, the patient must wait 30 days before enrolling.
- 3.2.4 Pregnant participants will not be entered on this study given that the effects of Metformin on the developing human fetus are unknown.
- 3.2.5 Breastfeeding mothers are not eligible because there is an unknown but potential risk for adverse events in nursing infants secondary to treatment of the mother with Metformin.
- 3.2.6 Patients must not have a history of allergic reactions attributed to compounds of similar chemical or biologic composition to Metformin.
- 3.2.7 Patients must not have uncontrolled intercurrent illness including, but not limited to, ongoing or active infection, symptomatic congestive heart failure, unstable angina pectoris, cardiac arrhythmia, or psychiatric illness/social situations that would limit compliance with study requirements.
- 3.2.8 Patients must not have prior history of symptomatic hypoglycemia over the past year or hypoglycemia with glucose <50mg/dL on screening and baseline laboratory assessments.
- 3.2.9 Patients must not have type 1 diabetes mellitus.

- 3.2.10 Patients must abstain from alcohol as part of this study.
- 3.2.11 Patients must not have a diagnosis of myelodysplastic syndrome or leukemia, or other concurrent malignancy undergoing treatment.
- 3.2.12 Patients must not have vitamin B12 deficiency.
- 3.2.13 Patients must not have G6PD deficiency.

3.3 Inclusion of Children and Minorities

Both male and female children of all races and ethnic groups are eligible for this trial.

4 ENROLLMENT PROCEDURES

4.1 General Guidelines

Eligibility screening: Available laboratory test results which are standard of care, such as CBC with differential, chemistries, LFTs, and prior bone marrow aspirate/biopsies, will be carefully reviewed to determine the participant's eligibility for the study prior to the patient signing consent (see section 3).

Baseline Assessments: Following the patient's consent, baseline laboratory assessments will be drawn and are detailed in Section 5.3 (study visit procedures) and section 5.7 (schedule of assessments). An investigator will confirm eligibility criteria and will complete and sign the protocol-specific eligibility checklist. If patients no longer meet eligibility criteria based on their baseline assessments, they will be considered screen failures. If one of these patients later meets eligibility criteria, the patient can be re-screened for enrollment. In these instances, the baseline and eligibility tests would need to be repeated except for G6PD.

Following enrollment, participants may begin protocol therapy and should begin protocol therapy within 14 days. Issues that would cause treatment delays should be discussed with the Overall Principal Investigator (PI). Specific baseline laboratory tests including CBC with differential, chem 10, and LFTs must be repeated prior to dosing on Day 1 if obtained >14 days prior to Day 1. The rest of the Day 1 assessments are detailed in Section 5.3 (study visit procedures) and section 5.7 (schedule of assessments).

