5.3.1 Visit 1: Baseline laboratory assessments – *BCH visit* (Day -28 to -1)

- Obtain informed consent
- Medical history
- Physical examination
- Lansky/Karnofsky Performance Status
- Height and weight
- Vital Signs
- Laboratory assessments: hematology (CBC with differential and reticulocyte count), chemistry (chem 10, LFTs), vitamin B12, G6PD, blood glucose, insulin level, oral glucose tolerance test, IGFBP-1, chromosomal breakage test, iron studies, hemoglobin electrophoresis
- Urinalysis
- Serum or urine pregnancy test
- Biomarker: bone marrow aspirate/biopsy
- Biomarker: aldehyde analyses
- Biomarker: buccal swab
- Distribution of drug diary

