5.3.2 Visit 2: Initiation of therapy (Day 1)

- Drug administration: if the subject does not live locally and cannot pick up the study drug from BCH, drug will be shipped to the subject's home. Day 1 will be considered the day that the subject takes the study drug for the first time.

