5.5 Criteria for Taking a Participant Off Protocol Therapy

Duration of therapy will depend on individual response, evidence of disease progression, and tolerance. Treatment may continue for up to 6 months from study entry and completion of planned follow-up, or until one of the following criteria applies:

- Diagnosis of myelodysplastic syndrome or leukemia
- Worsening of cytopenias as defined by one of the following, sustained over 8 weeks in duration:
 - Increase in transfusion requirement by two-fold
 - Decrease in hemoglobin by $>1.5\text{g/dL}$ and absolute value $<10\text{g/dL}$
 - Platelet count $<50\%$ of baseline value and absolute value $<100\text{k}$
 - ANC $<50\%$ of baseline value and absolute value <1000
- Intercurrent illness that prevents further administration of treatment
- SAE or other toxicity that meets criteria for removal from protocol therapy (see Section 7)
- Participant demonstrates an inability or unwillingness to comply with the oral medication regimen and/or documentation requirements

- Found to be ineligible, including participants who have repeat organ function laboratory at the baseline assessment which no longer meet eligibility criteria.
- Participant decides to withdraw from the protocol therapy
- General or specific changes in the participant's condition render the participant unacceptable for further treatment in the judgment of the treating investigator
- Withdrawal of consent for treatment or treatment and data submission
- Death

The reason for taking a participant off study, and the date the participant was removed, must be documented in the case report form (CRF).

Participants will be removed from the protocol therapy when any of these criteria apply. The reason for removal from protocol therapy and the date the participant was removed must be documented in the case report form (CRF).

In the event of unusual or life-threatening complications, treating investigators must immediately notify the Overall PI.

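### The pre-dose recheck in Section 4.1 does not name the pregnancy test, so that test can be up to 28 days old at first dose; 4.1 and 5.5 also need one disposition for a failed repeat

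*Combined protocol and SAP*

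**What the plan says.** Section 4.1 sets a recheck between enrollment and first dose: "Specific baseline laboratory tests including CBC with differential, chem 10, and LFTs must be repeated prior to dosing on Day 1", where the results on file are more than 14 days old. No other test is named.

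On pregnancy, Section 3.2.4 states: "Pregnant participants will not be entered on this study". It gives as its reason that the drug's effects on the fetus are not known. Section 5.3.1 lists "Serum or urine pregnancy test" at Visit 1, in the window Day -28 to -1. The next pregnancy tests are at Visit 8 (5.3.8, Day 85 ± 7) and Visit 11 (5.3.11). The pregnancy row of the 5.7 table carries the same three marks.

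Visit 2 (5.3.2) contains drug administration only. If a subject lives at a distance and "cannot pick up the study drug from BCH, drug will be shipped to the subject's home", Day 1 is the day the first dose is taken.

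On a failed result, 4.1 says: "If patients no longer meet eligibility criteria based on their baseline assessments, they will be considered screen failures". The off-therapy list in 5.5 includes: "Found to be ineligible, including participants who have repeat organ function laboratory at the baseline assessment which no longer meet eligibility criteria".

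**The concern.** By setting a 14-day limit for blood counts, chemistry and liver tests, the plan accepts that results from the far end of the 28-day window are too old to support a first dose. It sets no such limit for the pregnancy test, although pregnancy status can change within that window and the stated reason for the exclusion is exposure to the drug. What is at stake is whether an exclusion is verified close to the moment at which it protects anyone.

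The second issue is bookkeeping. If a repeat fails after enrollment but before dosing, the plan gives two candidate labels: screen failure, or enrolled and taken off therapy. The site needs one label so that participant flow is reported consistently.

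**Working it through.** The plan states no figure on this point, so there is none to reproduce. The check is day arithmetic on the stated windows, followed by a comparison of the two disposition rules.

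**Inputs**
- Visit 1 window: Day -28 to Day -1 (5.3.1, 5.7).
- First dose: Day 1 (5.3.2). I assume there is no Day 0.
- Recheck trigger: "must be repeated prior to dosing on Day 1 if obtained >14 days prior to Day 1" (4.1).
- Next pregnancy test: Day 85 ± 7, that is, Day 78 to Day 92 (5.3.8).

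**Age at first dose.** With no Day 0, a test on Day -k is k days old on Day 1.
- Named blood tests: a draw on Day -15 is 15 days old and is repeated; a draw on Day -14 is 14 days old and stands. The maximum age is therefore 14 days. The trigger covers Day -28 to Day -15, which is 28 - 15 + 1 = 14 of the 28 window days. This is a share of days, not of patients.
- Pregnancy test: no trigger applies, so the maximum age is 28 days, twice that of the named tests.

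**Interval between consecutive pregnancy tests.** From Day -k to Day D it is k + D - 1 days.
- From Day -28: 28 + 78 - 1 = 105, 28 + 85 - 1 = 112, and 28 + 92 - 1 = 119 days.
- With a 14-day limit, the longest interval runs from Day -14 to Day 92: 14 + 92 - 1 = 105 days.

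The limit thus takes 119 - 105 = 14 days off the longest interval. The rest is set by the timing of Visit 8 and is not a measure of this gap.

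**Disposition.** Section 4.1 runs in order: baseline assessments, confirmation of eligibility with a signed checklist, enrollment, then the recheck. The screen-failure rule sits in the paragraph before enrollment. The recheck sits in the paragraph after it and has no disposition of its own. The 5.5 bullet speaks of a repeat laboratory, which suggests the later stage, but places it at the baseline assessment, which is the stage 4.1 assigns to screen failure.

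**Effect on the analysis sets.** Section 9.7 admits to the safety set anyone who took at least one dose. A patient caught before dosing is outside it under either label. A patient dosed and then removed within the first month as ineligible, for a reason unrelated to study drug, is in the safety set but is not evaluable for response under 4.2. The rule of 3 responders among 22 evaluable patients in 9.2 is untouched.

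**The case against.** The strongest case is that the plan already has the safeguards. The list in 4.1 is open-ended, so a pregnancy test could be included. An investigator confirms eligibility and signs a checklist. Requiring a repeat before dosing makes little sense unless the result is used. Contraception is a condition of entry (3.1.5.5). Exclusion 3.2.4 refers to entry rather than to first dose. And 4.1 and 5.5 can be read in sequence, before and after enrollment.

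Much of this stands, and it limits the point. It does not remove it: nothing in the documents adds the pregnancy test to the repeat, a contraception agreement is not a test, and the checklist is described before the recheck. The sequential reading of 4.1 and 5.5 is possible, but the reference in 5.5 to the baseline assessment works against it.

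A reader might also infer more than the text supports:
- *That a patient can start on 28-day-old blood tests.* Section 4.1 rules this out for CBC, chem 10 and LFTs. Of the tests discussed here, the 28-day figure applies only to the pregnancy test.
- *That the lack of a blood draw at Visit 2 contradicts 4.1.* Section 4.1 says "The rest of the Day 1 assessments are detailed in Section 5.3 (study visit procedures) and section 5.7 (schedule of assessments"). The recheck is specified in 4.1 itself, is conditional, and can be drawn before Day 1. A footnote would help, but its absence is missing detail.
- *That a remote patient already holds the drug when the recheck is done.* Section 5.3.2 allows shipment but does not say when it occurs relative to the recheck.
- *That the 17-week interval (119 days) shows the size of the problem.* It would still be 15 weeks (105 days) after the change.

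**Conclusion.** The point holds in a limited form. For participants of child-bearing potential, the plan as written allows a pregnancy test up to 28 days old at first dose, against at most 14 days for the blood tests that 4.1 names. This assumes no Day 0, a Visit 1 test on the first day of its window, and the list in 4.1 read as the tests it names. The documents do not show how many participants this would affect or that it has happened.

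Sections 4.1 and 5.5 give different dispositions for a failed result and must be reconciled. The documents do not settle which should apply to a repeat that fails after enrollment and before dosing. The lack of an explicit sentence on reviewing repeat results before the first dose is a smaller gap of detail. No sample size, power, error rate or primary analysis is affected.

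**What to change.** 1. In 4.1, add the serum or urine pregnancy test, for participants of child-bearing potential, to the tests repeated when more than 14 days old at Day 1.
2. In 5.3.2 and the Visit 2 column of 5.7, add a conditional footnote for the 4.1 recheck, with a local laboratory allowed.
3. In 4.1, state that repeat results are checked against Section 3 before the first dose.
4. Reconcile the screen-failure sentence in 4.1 with the 5.5 bullet, so that a repeat failing after enrollment and before dosing has one stated disposition.

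The cost is amendment wording, one urine test for some participants, and a short wait for results. The blood draws are already mandatory under 4.1.
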